symptoms that occur in the absence of prominent mood symptoms.” Inclusion of patients with chart diagnoses of schizoaffective disorder will require documentation of symptoms and a history consistent with a diagnosis of bipolar disorder, the absence of a history of psychotic symptoms in the absence of prominent mood symptoms, and the judgment of both the Research Team and the patient’s mental health provider that the most appropriate diagnosis is bipolar disorder, not schizoaffective disorder.

Participation will also require concurrence from the patient’s mental health provider and a notification to the provider responsible for the patient’s general medical care. The rationale for this requirement is to ensure that the mental health providers concur with the Research Team’s evaluations related to inclusion/exclusion criteria, that they are not aware of additional information not included in the medical record that may affect eligibility, that treatment with study medication is compatible with any planned modifications in treatment, and that the providers are committed to working with the Research Team to manage the patient during the course of the study.

If there is a prescribing mental health provider (MHP) we will require that concurrence is obtained from that mental health provider. However, if there is no prescribing mental health provider involved with the participant at the beginning of the study or if one is lost during the study, a mental health provider who is able to prescribe medications and who is able to assume care of the participant at Month 12/End of Study will be identified. At end of study at a “warm handoff”, the mental health provider is un-blinded. With the participant, they can continue or taper off lithium or start lithium (in the event they have been on placebo). The research team ensures that a prescribing mental health provider is involved prior to the warm handoff and that a mental health provider will be identified prior to study Month 10. Notification to the provider responsible for the patient’s general medical care alerts the provider to the patient’s involvement in the study. In addition, it should acknowledge the presence of any medical conditions or medications that may require additional monitoring during the course of the trial.

Exclusion Criteria

Potential subjects will be excluded if they have:

1. Schizophrenia

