On the basis of studies that examined associations between suicide rates and lithium concentrations in drinking water, it has been suggested that lithium may have a preventive effect even at very low plasma levels (Helbich et al., 2012; Kabacs et al., 2011; Kapusta et al., 2011; Ohgami et al., 2009; Schrauzer & Shrestha, 1990). Based on these reports and absence of data

for what constitutes a lower limit for effective plasma levels, dose (and plasma-level) reductions will be allowed for patients who are unable to tolerate 0.6-0.8 mEq/L. The lowest allowable dose of lithium for continued treatment will be 300 mg/day. All patients able to tolerate that dose will be maintained at the highest tolerable plasma level not to exceed 0.6-0.8 mEq/L.

Blinding

This is a double blind placebo-controlled study in which the participant, treating clinicians, and all study personnel, including the Central Psychiatrist/Safety Officer, are blinded to treatment assignment.

All investigators and Outcomes Adjudication Committee members will only see blinded interim reports. Members of the DMC will receive unblinded reports in that they will view study results by treatment group (e.g. A versus B) and these designations will be randomly assigned within a report. The placebo will be produced by the CSPCRPCC and be nearly identical in appearance to the active agent and have similar taste and odor.

Breaking the blind, to the patient's mental health provider, at the end of a participant's time in the study should not compromise the blind for the personnel at the study site nor influence outcome assessments of participants remaining in the study. All ratings and assessments will be completed before the blind is broken. To ensure that the breaking the blind on those who complete the study does not reveal information about the assignment of the last subjects, block randomization is within multiple strata and an extra treatment assignment will be inserted to each stratum of four to disrupt the blocks and mask block sizes, as described in Section VII.

Titrating study medication

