At the conclusion of the 1-year study treatment, participants will be referred to their treating mental health provider for continued management. There are data to suggest that suicidality and mood disturbances may be increased after stopping lithium. To insure continuity, the appointment with the subject's providers will be scheduled well before completion of the study. The Research Team will maintain responsibility for the subject until they have been seen by their treating clinician in a face-to-face encounter; the goal will be to provide warm-hand-offs through encounters that include the Research Team, the clinical provider, and the patient whenever possible. The research team will ensure that each study participant has a prescribing mental health provider assigned to him/her prior to study Month 10.

At the End of Study visit, the participant and the treating mental health provider will be informed of the treatment assignment. They will be reminded about the possible risks associated with rapid withdrawal of lithium and the need for a slow taper if lithium is to be discontinued. Patients will be asked to return for a 30-day follow-up study visit.

Patients who withdraw consent

Participants withdrawing consent will be asked to participate in a final study assessment. The blind will be broken at the time of this assessment and no further data will be collected. The Research Team will contact the participant's treating mental health provider to recommend gradual tapering of lithium as needed.

Patients who discontinue study treatment prior to 1 year

The investigator may discontinue the study medication for any reason, including adverse effects, safety concerns or protocol violations. In addition, participants may elect to discontinue study medication at any time. Discontinuation of study medication will not automatically result in withdrawal of the participant from the trial, nor unblind the study treatment. The investigators will encourage the participant to continue with study assessments but they will not be required to complete EKGs, blood draws or vital signs except for the 30 day follow-up visit (see Table 7). If a participant does not agree to continue assessments, the blind will be broken, to the participant's mental health provider, at the time they are tapered or discontinued. All ratings and assessments will be completed before the blind is broken.

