7. Managing or reporting of adverse events or serious adverse event, and when questions arise, in consultation with the Site Physician, Clinical Research Pharmacist, Study Chair, or Study Director.

Definitions

For CSP#590, AE and SAEs will be collected using the International Conference on Harmonisation (ICH) Clinical Safety Data Management (ICH-E2A) and CSP Global Standard Operating Procedure (SOP) 3.6.2 definitions as follows:

Adverse Events: An AE is any untoward physical or psychological occurrence in a human subject participating in research. An AE can be any unfavorable and unintended event, including an abnormal laboratory finding, symptom, or disease associated with the research or the use of a medical investigational test article. An AE does not necessarily have to have a causal relationship with the research.

Serious Adverse Events: An SAE is an adverse event that results in:

- Death
- A life-threatening experience,
- Inpatient hospitalization
- Prolongation of hospitalization,
- Persistent or significant disability/incapacity,
- Congenital anomaly/birth defect, or
- Requires medical, surgical, behavioral, social, or other intervention to prevent such an outcome.

Relatedness: Relatedness involves an assessment of the degree of causality between (or attributed to) the *study intervention* and the event. Site investigators are charged with making an assessment of relatedness based on their clinical judgment and experience. The assessment of relatedness provided by the site investigator is used by the sponsor (CSP) to determine if an AE/SAE represents an alteration or change in the safety profile of the study intervention. All AE/SAEs with a reasonable causal relationship to the investigative treatment may be considered “related”. A definitive relationship does not need to be established.

Adverse Events and Serious Adverse Events Reporting Requirements

Adverse Events: Only adverse events possibly or definitely related to the study intervention will be reported. Documentation of this assessment may be recorded on a worksheet or source document. The lithium carbonate formulation used in CSP #590 is a commercially available product prescribed for bipolar disorder. Lithium has a well characterized adverse effect profile and there is no evidence suggesting this agent will demonstrate a different adverse event profile in CSP#590 from the one already known.

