Serious Adverse Events: All SAEs shall be collected for CSP #590 regardless of relatedness; however, the Site Investigator must still make an assessment of whether or not the event is related to the study intervention. All SAEs will be recorded on the appropriate case report form. SAEs that meet the criteria for an endpoint should be reported as such.

Adverse Event and Serious Adverse Event Monitoring

Patients will be actively monitored at each clinic visit and telephone contact for AEs and SAEs. All AEs and SAEs will be recorded on the appropriate event form(s). Per CSP policy, active and passive monitoring of AEs and SAEs will begin when a participant signs the Randomization Informed Consent. Monitoring of AEs and SAEs will continue through to 30 days past the “end of study” for each study subject. (No SAEs should be collected for participants after withdrawal of consent).

Expedited Reporting of Serious Adverse Events to CSP

All SAEs will be promptly reported by reporting the event via the CSP #590 Electronic Data Capture (EDC) system *within 72 hours* of the Site Investigator or other study personnel being made aware of the event. Email notification of the submission is relayed by the EDC system to the study Biostatistician, Clinical Research Pharmacist, Study Director, and Study Chair. The CSP #590 Clinical Research Pharmacist (CRP) is responsible for evaluating all SAEs for immediate patient safety concerns. A back-up CRP will evaluate the event in if the primary CRP is not available.

Reporting of Serious Related and Unexpected Events

The determination of the expectedness of an event is the responsibility of the CSP. The source of information used in the determination of expectedness includes the CSP #590 Drug Information Report, the Informed Consent form, and published literature. SAEs determined by the CSP to be both related to the study intervention and unexpected after review by the CRP, the Study Chair, and consultants as needed will be reported to the VA Chief Research and Development Officer, the FDA, and site investigators.

Reporting of Adverse and Serious Adverse Events to the DMC

The Coordinating Center and CSPCRPCC will summarize blinded and unblinded AE and SAE data for the DMC in a format and on a schedule requested by the DMC. The DMC will receive results by treatment group (e.g. A versus B) but will not receive fully unblinded reports until all data collection has been completed.

Reporting Requirements of the VA Central IRB

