10.1. Interim Analysis	
10.2. Futility Analysis	
11. Final Statistical Report.....	page 24
12. References.....	page 25

1. Introduction

This document outlines the statistical methods for the analysis of data collected in the Department of Veterans Affairs Cooperative Studies Programs (CSP) study #590 entitled “A Randomized double-blind placebo-controlled trial of lithium augmentation and enhanced suicide prevention management in preventing suicide re-attempts in individuals with depression and bipolar disorder.” The purpose of this document is to provide guidelines from which the analysis will proceed. Deviations from these guidelines will be documented and filed electronically in the study central file Sharepoint site.

The following documents were used in preparation of this statistical analysis plan (SAP):

- Clinical Study Protocol CSP #590
- Case Report Forms (CRF) from above entitled Protocol
- Global CSP SOP 2.9: “Developing and Conducting Statistical Analyses
- Local Work Instruction WI 201Statistical Analysis Plan and Biostatistical Research Data Processing Plan Creation and Amendment
- Local Job Aid No. 5: Guide to Writing Statistical Analysis Plans

2. Overview of the Study Design and Study Objectives

This is a double-blind, placebo-controlled randomized clinical trial that will assess the effectiveness of lithium augmentation to enhanced usual care for prevention of repeated fatal and non-fatal suicide attempts in participants with bipolar disorder or depression who have survived a recent episode of suicidal self-directed violence.

A total of 1862 subjects recruited from 29 Veterans Health Administration (VHA) centers over a 3 year period are expected to be randomized equally to lithium (Lithium ER) or placebo. Participants will be followed actively for 12 months from randomization. Adverse event monitoring for safety will be for one additional month beyond active follow up, i.e., up to 13 months.

The primary hypothesis is that lithium is superior to placebo for the prevention of episodes of suicidal self-directed violence over time. The primary outcome measure is time from randomization for treatment allocation to any first episode of suicide attempt, interrupted attempt, hospitalization specifically to prevent suicide, or death from suicide.

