7.4. Safety Data

Safety information to be collected for this study include description of the event, distinction between serious and non-serious adverse event, severity and expectedness of the event, relatedness to the study intervention, and outcome of the event. In addition, data on all events will be classified using the Medical Dictionary for Regulatory Activities (MedDRA) (Version 9.0) coding dictionary.

Safety data will be collected for all consented subjects from the date the first consent was signed up to 13 months post randomization for related non-serious adverse events, and all serious adverse events. If the subject terminates from the study prior to 13 months post randomization date, collection of safety data will cease on termination date.

For reporting to the DMC and inclusion in the final report safety data will be aggregated for the ITT analytic sample only as described in **3.3**. Data will be summarized as follows.

- Frequency and percentages of related non-serious and all serious adverse events overall and by intervention group
- Frequency and percentages of all unique subjects with non-serious and serious adverse events overall and by intervention group
- Rates of non-serious and serious adverse events overall, by intervention group, and by center, calculated as # events/ person-time in years
- Tabulation of event type, MEDRA classification, severity, expectedness, relatedness and outcome of all events overall and by intervention group
- Overall hospitalization, suicide reattempt, and mortality rates at 1 year overall and by intervention group

8. Data Monitoring Committee Reports

Data and study progress will be monitored by the study executive committee and by the Data Monitoring Committee (DMC). The DMC will review the study progress and safety semi-annually with additional meetings and communications as needed. All reports will be generated using SQL and SAS.

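### SAP 7.4 pools adverse events from the 30 days after unblinding and the end of randomised treatment with the blinded year in the by-arm safety summaries, with no split by period

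*SAP*

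**What the plan says.** **Safety window.** SAP 7.4: "Safety data will be collected for all consented subjects from the date the first consent was signed up to 13 months post randomization". SAP section 2 gives the same length: "Adverse event monitoring for safety will be for one additional month beyond active follow up, i.e., up to 13 months". Protocol XV agrees on the end point: "Monitoring of AEs and SAEs will continue through to 30 days past the" end of study for each subject.

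**Unblinding.** Protocol XIV, on participants who complete one year: "At the End of Study visit, the participant and the treating mental health provider will be informed of the treatment assignment". It then adds: "Patients will be asked to return for a 30-day follow-up study visit". The 30-day visit therefore follows disclosure.

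**Treatment after hand-off.** SAP 3.2 ends the intervention at 12 months. From that point the choice is open in both arms. Protocol V (rationale for the inclusion criteria) says of the mental health provider: "With the participant, they can continue or taper off lithium or start lithium", the last option being for those who had been on placebo.

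**What is tabulated.** SAP 7.4 lists AE and SAE counts, subjects with events, events per person-year and event classifications by intervention group. None is divided at unblinding or at the end of treatment. One bullet is limited in time: hospitalization, reattempt and mortality rates are given at 1 year. The closed-session DMC tables listed in SAP 8.3.5 name no period split.

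**Which events count.** For non-serious events, Protocol XV says: "Only adverse events possibly or definitely related to the study intervention will be reported". SAEs are collected regardless of relatedness.

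**Ratings and the blind.** Protocol XIII (Blinding) says of disclosure at the end of a participant's time in the study: "All ratings and assessments will be completed before the blind is broken". Protocol XIV repeats the sentence for those who discontinue early. Tables 6 and 7 nevertheless schedule the Columbia scale, PHQ-9 and ISS at the 30-day visit.

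**The concern.** A by-arm safety table is normally read as a comparison of assigned treatments under blinding. Here that reading holds up to the End of Study visit and not beyond it. Three things change together at hand-off: the participant who reports events knows the arm, the assigned drug is no longer the protocol treatment, and either arm may be on or off lithium.

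The documents themselves give reasons to expect that month to differ. Protocol XII reports that about three quarters of people have some side effect on beginning lithium. It also discusses a rise in suicide-related behaviour after lithium is stopped, and Protocol XIV repeats that caution at hand-off. Since any inpatient admission is an SAE, an admission during a post-study taper enters the lithium column beside on-drug events. An SAE in a former placebo participant who has just started lithium enters the placebo column.

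At stake is how the AE and SAE comparison is interpreted. The efficacy result is not involved.

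**Working it through.** **1. Reproduce the plan's figures.** Active follow-up is 12 months plus one safety month: 12 + 1 = 13 months, as stated in SAP section 2 and SAP 7.4. For attrition, Protocol VII takes 40% uniform dropout as a 20% data loss: 1862 × 0.80 = 1489.6, stated as 1490.

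**2. Share of safety person-time after unblinding.** Let N = 1862 be the number randomised and d the proportion dropping out uniformly over the year.
- Blinded year: Y = N × (1 − d/2) person-years.
- Following month: M = N × (1 − d)/12, because under SAP 7.4 safety collection stops at termination and only those followed to End of Study contribute.
- Share = M/(Y + M).

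| Dropout d | Y | M | Share |
|---|---|---|---|
| 0 | 1862.0 | 155.2 | 7.7% (= 1/13) |
| 40% (planning value) | 1489.6 | 93.1 | 5.9% |
| 58% (lithium-arm attrition in the earlier placebo-controlled trial, Protocol VII) | 1322.0 | 65.2 | 4.7% |

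This treats 30 days as one twelfth of a year and takes unblinding to occur at month 12. Protocol XIV lets the completion visit fall up to a month late, so individual dates will vary.

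**3. Possible effect on a rate ratio (illustration).** The documents give no AE rates for the trial, so these are assumptions. Suppose the blinded-year lithium-to-placebo rate ratio is 2.0. In the last month both arms have the same rate, equal to k times the blinded-year placebo rate. With equal person-time per arm and 40% dropout, Y/M = 1489.6/93.1 = 16, so

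pooled ratio = (2.0 × 16 + k)/(16 + k).

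- k = 1: 33/17 = 1.94
- k = 2: 34/18 = 1.89
- k = 3: 35/19 = 1.84

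In the placebo arm the last month then supplies k/(16 + k) of the events: 5.9%, 11.1% and 15.8%. These values show the order of the effect and do not bound it. The true last-month ratio could lie on either side of 1.0.

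**4. The statements on ratings.** Protocol XIII puts all ratings before the blind is broken. Protocol XIV discloses the arm at End of Study and then asks for a 30-day visit, at which Tables 6 and 7 schedule ratings. Both cannot be literally true for someone who attends that visit after disclosure.

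**The case against.** The strongest reply is that a 30-day safety tail compared by assigned arm is ordinary practice and useful here. Protocol XII lists reactions on stopping lithium among the risks of participation, and cutting the table at End of Study could hide them. This stands against dropping the month. It does not stand against showing the month separately, where withdrawal-period events are easier to see.

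It can also be said that the most consequential rates (hospitalization, reattempt, mortality) are already limited to 1 year, that early terminators leave safety collection at termination, and that DMC table shells are kept outside these documents (SAP 8.2) and may contain a split. All of this is correct. It narrows the point to the AE and SAE summaries for participants who reach End of Study.

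A reader might infer more than the documents support:

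- *That the 30-day ratings sit in the by-arm safety tables.* They do not. Psychometric measures belong to SAP 7.3 and, for the ISS and Columbia scale, to secondary objective 4.
- *That objective 4 uses the 30-day ratings.* SAP 5.3 speaks of each follow-up visit without naming them, but Protocol VI (Other Outcomes) sets secondary outcomes within 12 months. The wording needs a clarification and is not evidence of a planned misuse.
- *That start-up effects would add many points to the placebo column.* Multiplying 75% by an assumed uptake of 10%, 20% or 40% gives 7.5, 15 or 30 points. The uptake figures have no source in the documents. At 40% dropout only 60% reach hand-off, which gives 4.5, 9 or 18 points of all randomised. Non-serious events must also be judged related to the study intervention, and lithium begun by the provider after hand-off arguably is not. The size cannot be stated.
- *That relatedness is judged unblinded.* Site investigators judge it, and Protocol XIII says disclosure to the provider should not compromise the site's blind. Protocol XIV wants the research team at the hand-off where possible, so leakage can happen, but it is not the plan.

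**Conclusion.** The point holds in limited form. For participants who reach End of Study, AEs and SAEs of the following 30 days arise after disclosure of the arm and after randomised treatment, and SAP 7.4 adds them to the blinded year by arm with no period split. The affected share is about 5.9% of pooled person-time under the plan's own 40% uniform dropout, with a range of 4.7% to 7.7%. On assumed rates, a ratio of 2.0 moves to between 1.84 and 1.94. This is a modest blurring of a descriptive safety comparison, and its direction cannot be known in advance. The primary endpoint ends at 12 months, so its analysis, type I error and power do not change.

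The safety tail is not itself a mistake. What is missing is the split, together with a clear statement of which visits feed the secondary rating analyses. The conflict over ratings and the blind is one of wording and should be reconciled.

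**What to change.** 1. In SAP 7.4, report AEs and SAEs by arm (counts, subjects affected, events per person-time) from randomisation to the end of randomised treatment or unblinding. Use each participant's own date, since the completion visit has a wide window.
2. Tabulate the following 30 days separately by arm, with their own person-time and, where recorded, by whether lithium was continued, stopped or started. Withdrawal-period events then stay visible. Apply the same split to the closed-session DMC tables if the shells lack it.
3. State in SAP 5.3 that the 30-day ratings do not enter the objective 4 model, in line with the 12-month limit in Protocol VI, and say in SAP 7.3 whether they are summarised.
4. Reconcile the sentence in Protocol XIII and XIV on completing ratings before the blind is broken with the 30-day columns of Tables 6 and 7.
5. While editing, reconcile two neighbouring differences. Safety collection starts at the first consent in SAP 7.4 but at the randomization consent in Protocol XV. It stops at termination in SAP 7.4, while Protocol XIV has a 30-day safety evaluation for those who discontinue treatment because of an adverse effect or other event.

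The cost is SAP wording, one additional table and a protocol clarification, with no new data. The downside is slightly less person-time in the main safety comparison: about 93 of 1583 person-years (1489.6 + 93.1 = 1582.7) at the planned dropout. Settling the split before results are seen by arm avoids a post hoc choice.

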- 2) There are no impending safety issues posed to the participant after his or her death that would otherwise require unblinding

Release of information regarding study-related matters should never occur with any persons outside the study team, given that:

- 1) A Certificate of Confidentiality is in place for CSP 590. This protects participants' privacy by withholding information from anyone not connected with the conduct of the research study to avoid disclosure of information that may have adverse consequences. Because of this, the research team is not compelled in any Federal, State, or local civil, criminal administrative, legislative or other proceedings to provide information about the participant.
- 2) The HIPAA authorization form that participants sign at the beginning of the study protects their privacy and does not allow us to release information.
- 3) No written consent to disclosures is provided by the participant in conjunction with study participation.

See tables below for specific detail on Notifications and Procedures for Participant Deaths.**NOTIFICATIONS**

Activity	Responsible Party	Considerations/ Requirements	Recommendation
Notification of Coordinating Center	Site Study Staff	Protocol	Reported via EDC system within 72 hours of the Site Investigator being made aware of the event. Email notification of the submission is relayed by the EDC system to the study Biostatistician, Clinical Research Pharmacist, Study Director and Study Chair.
Notification of CSPCC Study Staff and Director	Study Director, Clinical Research Pharmacist		
Notification of VA Central Office	CSPCRPCC, CSPCC	CSP SOP 3.6	Reported via email by Close of Business the next day after becoming aware of the event with a full report sent via email within 15 business days of the initial CO notification.
Notification of VA Central IRB	Site Study Staff, Chair's Office	CIRB Table of Reporting Requirements	-If suicide , expedited reporting is not required as this is an anticipated outcome. These SAEs are reported at continuing review. -If " unanticipated *and* related " to research, expedited reporting is required (within 5 business days of becoming aware of the occurrence). -Otherwise SAE is reported at continuing review.

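### The by-arm all-SAE totals include SAEs that are also primary-endpoint events, so a working lithium would partly hide other serious harms in them; one extra row would show the contrast directly

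*SAP*

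**What the plan says.** **What counts as an SAE.** Protocol XV, Definitions, begins "An SAE is an adverse event that results in" and lists death and inpatient hospitalization among the criteria. The reporting requirements in the same section add "All SAEs shall be collected for CSP #590 regardless of relatedness" and then "SAEs that meet the criteria for an endpoint should be reported as such". For a participant's suicide, the notification table in Protocol XIV says "expedited reporting is not required as this is an anticipated outcome. These SAEs are reported at continuing review", so suicides are treated as SAEs.

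**What counts as an endpoint.** SAP 4.2 lists non-fatal attempts, interrupted attempts, hospitalizations to prevent suicide and suicide deaths. It says potential endpoints come mostly through SAE reporting or the Columbia follow-up form.

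**What is tabulated.** SAP 7.4, for the DMC and the final report, lists:
- bullet 1: "Frequency and percentages of related non-serious and all serious adverse events overall and by intervention group"
- bullet 2: "Frequency and percentages of all unique subjects with non-serious and serious adverse events overall and by intervention group"
- bullet 3: "Rates of non-serious and serious adverse events overall, by intervention group, and by center", per person-year
- bullet 4: "Tabulation of event type, MEDRA classification, severity, expectedness, relatedness and outcome of all events overall and by intervention group"
- bullet 5: one-year hospitalization, reattempt and mortality rates by arm

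In SAP 8.3.5 (closed session), D2 and D4 show SAEs by treatment, D5 and D6 show related non-serious events and SAEs by organ class, and D7 shows deaths. Neither SAP 7.4 nor any of these table titles says that endpoint SAEs are left out or shown apart. The annotated table shells are kept outside the documents (SAP 8.2).

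**The concern.** Some events are counted both as efficacy outcomes and as serious harms. If lithium prevents suicidal events, its arm loses SAEs for a reason unrelated to tolerability. A true excess of renal, cardiac, neurological or other serious events on lithium would then be netted against that benefit in the overall SAE count, the percentage of subjects with an SAE and the SAE rate. The bias also runs the other way: if lithium raised suicidal events, the totals would overstate its other toxicity.

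This matters because Protocol XVII.C.III lists an excess of serious adverse events or mortality in either group as a ground for early termination. The by-arm totals are the figures most directly suited to that judgement, and they also go into the final report.

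**Working it through.** **Inputs from the documents.** One-year endpoint rates are 15% (placebo) and 9.45% (lithium) (SAP 4.3). There are 1,490 evaluable subjects, 745 per arm (SAP 10), and 373 per arm at the interim (SAP 10.1).

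**Plan's own figures.** HR = ln(1 − 0.0945)/ln(1 − 0.15) = 0.611, against the stated 0.61. Events = 745 × (0.15 + 0.0945) = 182, as in SAP Table 2. Power by the Freedman formula with HR 0.61 and 182 events is 90.2% at alpha 0.048, against the stated 90%. The inputs are reproduced.

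**Assumed inputs.** The documents do not give the share *f* of endpoint events that are SAEs. Interrupted attempts need not meet any SAE criterion, so *f* may be well below 1. The range 25% to 100% is used. The background SAE rate and any toxic excess are also assumed.

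**Offset in the all-SAE event total** = *f* × (0.15 − 0.0945) × n, counting first endpoint events only:

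| f | points | per 745 | per 373 |
|---|---|---|---|
| 25% | 1.4 | 10 | 5 |
| 50% | 2.8 | 21 | 10 |
| 75% | 4.2 | 31 | 16 |
| 100% | 5.55 | 41 | 21 |

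At *f* = 100% the offset per 745 is 0.045 × 745 = 34 for a 30% effect, 0.06 × 745 = 45 for a 40% effect, and 0 for no effect. Bullets 1 and 3 count every event, so repeat endpoint events would add to it.

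**Unique subjects (bullet 2).** A patient with another SAE is counted anyway, so the offset shrinks. With independent overlap and *f* = 100% it is 5.55 × (1 − b) = 5.3, 5.0, 4.4 or 3.9 points at a background SAE rate b of 5%, 10%, 20% or 30%.

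**What the total would show.** Displayed lithium-minus-placebo difference = 745 × (t − 0.0555*f*), for an assumed true excess t of other SAEs:

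| True excess | f = 25% | 50% | 75% | 100% |
|---|---|---|---|---|
| 3 points (+22) | +12 | +2 | −9 | −19 |
| 5.55 points (+41) | +31 | +21 | +10 | 0 |
| 8 points (+60) | +49 | +39 | +29 | +18 |

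The zero at 5.55 points and *f* = 100% is by construction.

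**Does the organ-class table already cover this?** Take a 3-point excess, 745 per arm, an assumed 1% background per class and an illustrative nominal two-sided 5% test (the SAP names no SAE test). Classes are treated as independent, so P(any class signals) = 1 − (1 − p)^k.

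| Classes affected (k) | Per class (p) | Any class signals | Row without endpoints, background k × 1% |
|---|---|---|---|
| 1 | 96% | 96% | – |
| 3 | 36% | 73% | 80% |
| 6 | 14% | 59% | 59% |

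Reading several classes raises the chance of a false lithium-excess signal to 1 − 0.975³ = 7% and 1 − 0.975⁶ = 14%, against 2.5% for a single row. A combined row therefore gives better error control and a cleaner summary, but little or no extra detection.

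**The case against.** The strongest reply is that the separating information is already planned. Bullet 4 tabulates MedDRA class, expectedness and relatedness by arm. Bullet 5 gives reattempt and mortality rates by arm, and D5 to D7 add class tables and deaths. Protocol XV lets the DMC set the format of its safety summaries, SAP 8.3 puts the table list up for discussion at the first DMC meeting, and endpoint SAEs are to be reported as endpoints, so the DMC can ask for the split. A total that contains every SAE is not a mistake.

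Most of this stands. A reader might infer that serious lithium toxicity would go unseen, or that diffuse toxicity would be missed by D6. The documents do not support either inference. Distinctive toxicity would appear by class, in relatedness, or in the DMC's review of high lithium levels (Protocol XIX.B). Diffuse toxicity can be picked up by reading across, or summing, the non-psychiatric classes. Nor can one infer that the tables as built lack the split, because the shells are not in the documents.

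Some of it does not stand. The instruction to report endpoint SAEs as such is directed at sites and follows directly on the rule that all SAEs are collected and recorded; it does not remove them from the tables. Bullet 5 rates cannot be subtracted from SAE counts, because not every reattempt is an SAE. None of the planned displays is an SAE total without endpoint events.

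**Conclusion.** The point holds in a limited form. As stated, the by-arm all-SAE totals in SAP 7.4 bullets 1 to 3 and in D2 and D4 mix efficacy events with other serious harms. If lithium works as designed, they understate an excess of other harms by about 10 to 41 first events per 745, depending on the assumed share of endpoint events that are SAEs. If lithium has no effect, the expected offset is zero. The overlap and the absence of a stated exclusion come from the documents; the share, the background rate and the toxic excess are assumptions.

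This is a gap in presentation, not an error in the plan. The affected reading is the headline SAE contrast, and much of the separation can be recovered from other planned tables. The value of the change is modest and its priority is optional to low. The primary analysis and the alpha allocation are unaffected.

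**What to change.** Keep every all-SAE row. Add to the SAP 7.4 summaries and to D4 (and to D2 if wanted) one by-arm row: SAEs excluding those adjudicated as primary endpoints. Until adjudication is complete, use the site-reported endpoint status and label the row provisional. Keep accidents, events of undetermined intent, non-suicidal self-directed violence and all study-medication poisonings in the row, and footnote how many of those poisonings are also endpoints.

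The cost is one row built from information the trial already collects. There are three downsides:
- The row is provisional at DMC meetings because of adjudication lag.
- It is not purely non-endpoint. At the roughly 1% a year given in Protocol VIII.F, study-medication overdoses would be about 0.01 × 745 = 7 participants per arm, and some offset remains if lithium also reduces the retained self-harm and accident events.
- By subtraction the DMC could see endpoint SAEs by arm outside the single planned interim test, although Study Outcomes (Table C1) is an open-session table. D6 and D7 already largely reveal this, so the added exposure is modest. The efficacy test stays at its one interim look at 0.002.
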